1.1.3 Rationale for the Study and Anticipated Risks

No approved therapeutic options are available for subjects who have progressive SCLC following treatment with two prior therapies, including at least one involving a platinum-based frontline regimen. Based on the promising efficacy data to date, rovalpituzumab tesirine warrants investigation as a potentially important therapeutic option in the third-line and later setting. This

study will examine the therapeutic utility of rovalpituzumab tesirine in subjects with DLL3+ extensive-stage SCLC after failure of at least two prior systemic regimens, including a platinum-based therapy.

Potential risks with rovalpituzumab tesirine include fatigue, dyspnea, and nausea, which have been the most frequently reported AEs to date. However, remarkable toxicities have included serosal effusions (typically pleural or pericardial), peripheral edema, cutaneous reactions (typically photosensitivity), and thrombocytopenia. In addition, preclinical toxicology studies conducted in the rat and the cynomolgus monkey have identified the lung and kidney as a potential source of clinical AEs. Accordingly, safety assessments will include regular assessments at protocol-specified time points of routine physical examination, laboratory and imaging tests, as well as echocardiograms, a fluid retention questionnaire, daily weights and spot urine protein testing.

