AE severity and seriousness are assessed independently. 'Severity' characterizes the intensity of an AE. 'Serious' is a regulatory definition and serves as a guide to the sponsor for defining appropriate regulatory reporting obligations (see definition for Serious Adverse Events).

Relationship of the Adverse Event to Study Treatment

The relationship of each AE to study drug should be evaluated by the investigator using the following criteria:

Related: There is evidence to suggest a causal relationship between the drug and the AE, such as:

- An event that is uncommon and known to be strongly associated with drug exposure (e.g., angioedema, hepatic injury, Stevens-Johnson Syndrome)
- An event that is not commonly associated with drug exposure, but is otherwise uncommon in the population exposed to the drug (e.g., tendon rupture)

Unrelated: Another cause of the AE is more plausible (e.g., due to underlying disease or occurs commonly in the study population), or a temporal sequence cannot be established with the onset of the AE and administration of the study treatment (latency), or a causal relationship is considered biologically implausible

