7.6.1.3 Reporting Periods for Adverse Events and Serious Adverse Events

The safety reporting period for all AEs and SAEs is from study Day 1 (during and post-dosing) up to 30 days after the last study treatment dose. For those undergoing retreatment, the safety reporting period will also include retreatment study Day 1 (during and post-dosing) up to 30 days after the last study retreatment dose. However, all study protocol-procedure related AEs and SAEs are to be recorded from the time of informed consent. Additionally, all SAEs that occur after the safety reporting period that are considered study treatment-related in the opinion of the investigator should also be reported to the sponsor or its designee.

Each SAE must be followed until the SAE is Recovered/Resolved, Not recovered/Not resolved, Recovered/Resolved with sequelae, or the subject dies (the SAE may be assessed as ongoing at the time of death). SAE outcomes may not be possible to collect when a subject withdraws consent and/or is lost to follow-up. All non-serious AEs will be followed through the end of the safety reporting period. Certain non-serious AEs of interest should be followed until resolution, return to baseline, or study closure.

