7.7.1 Treatment Emergent Adverse Events

All adverse events will be coded using the MedDRA dictionary. Safety analyses will involve examination of the incidence, severity, and type of treatment-emergent adverse events (TEAE) and serious adverse events as reported by the investigators. A treatment-emergent adverse event (TEAE)/treatment emergent serious adverse event is defined in Section 6. An applicable AE/SAE is considered ‘related’ if its relationship to study drug was judged by the investigator. Ongoing adverse events that have a change in severity, action taken with study drug, or outcome will be recorded multiple times with the

changes. If a subject has multiple occurrences of an adverse event with the same system organ class, the most severe event will be chosen. Similarly, if a subject has multiple occurrences of an adverse event with the same preferred term, the most severe event will be chosen. If a partial date does not provide enough information to determine the onset date relative to first dosing date, then the adverse event will be assumed as treatment-emergent, otherwise partial dates will be imputed relative to the first dose date. TEAEs will be summarized by system organ class and preferred term. These summaries will be presented by system organ class and preferred term for the following subsets:

- All TEAEs (All grades, and for maximum grade of 3 or 4)
- All TESAEs (All grades, and for maximum grade of 3 or 4)
- All TEAEs leading to study drug discontinuation (All grades, and for maximum grade of 3 or 4)
- All TEAEs leading to death

All drug-related TEAEs, and all drug-related TESAEs will also be summarized. The above tables will also be categorized by gender and age group (<65, \geq 65 years). For tables classifying TEAEs by severity, if a subject has multiple occurrences of an adverse event with the same system organ class, the most severe event will be chosen. Similarly, if a subject has multiple occurrences of an adverse event with the same preferred term, the most severe event will be chosen.

Adverse events of special interest (AESI) identified by the specific search criteria outlined in Appendix F will be summarized by System Organ Class (SOC) and Preferred Term (PT) [REDACTED]

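### The causality examples in Protocol Section 7.6.1.1 count commonness against relatedness, which steers frequent drug effects shared with the disease toward Unrelated

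*Protocol*

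**What the plan says.** Protocol Section 7.6.1.1, under the relationship of the adverse event (AE) to study treatment, gives the investigator two categories and no intermediate one.

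- **Related** opens with "There is evidence to suggest a causal relationship between the drug and the AE, such as" and lists two examples. The first is "An event that is uncommon and known to be strongly associated with drug exposure". The second is "An event that is not commonly associated with drug exposure, but is otherwise uncommon in the population exposed to the drug".
- **Unrelated** applies when another cause is more plausible, with the examples "due to underlying disease or occurs commonly in the study population". It also applies when timing does not fit or a causal link is biologically implausible.

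Section 1.1.3 describes the drug's own profile. It names "fatigue, dyspnea, and nausea, which have been the most frequently reported AEs to date", and separately lists serosal effusions, peripheral edema, skin reactions and thrombocytopenia as notable toxicities.

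The call is used later. SAP Section 7.7.1 takes relatedness from the investigator and states: "All drug-related TEAEs, and all drug-related TESAEs will also be summarized". Protocol Section 7.6.1.3 ends the safety reporting period 30 days after the last dose. Beyond that, the additional duty to report covers "all SAEs that occur after the safety reporting period that are considered study treatment-related" in the investigator's opinion.

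**The concern.** Wherever the examples mention frequency, they point the same way: uncommon supports Related, common supports Unrelated. None covers an event that is common in these subjects and is also a known effect of the drug. An investigator weighing such an event finds a printed reason to call it Unrelated and no matching example on the other side.

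Commonness is also listed as an alternative to underlying disease, so it reads as a ground of its own. A frequency is not a cause.

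At stake is a one-directional lean in the drug-related tables, in a trial with no control arm to supply a background rate. Late serious adverse events (SAEs) are also exposed: one called Unrelated falls outside the reporting duty, so the all-causality tables cannot be relied on to recover it. Section 3.2.2 reports delayed or cumulative toxicities in the phase 1 study, so late events are a practical matter here.

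**Working it through.** No arithmetic applies. The check sets the criteria against the drug's stated profile and then follows the relatedness call to each place that uses it.

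1. **Related examples.** The first needs an event that is uncommon. The second needs an event otherwise uncommon in exposed subjects. Fatigue, dyspnea and nausea, described as the most frequent AEs with this drug, fit neither if they are common in this trial.
2. **Unrelated example.** If those three events are common in the trial, they fit the commonness example directly.
3. **Circularity.** All treated subjects receive the drug, so the frequency seen in the trial is the disease background plus any drug excess. With no untreated arm, only the sum is observed. A drug effect frequent enough to matter makes the event common in the study population, and so meets an example of Unrelated. The criterion cannot separate the two sources.
4. **Where the call is used.**

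| Place | Depends on relatedness? |
|---|---|
| SAP 7.7.1, drug-related treatment-emergent AE and SAE summaries | Yes |
| Protocol 7.6.1.3, SAEs after the 30-day period | Yes |
| Protocol Table 5-2, Grade 3 or 4 non-albumin laboratory abnormality | Yes |
| Protocol 5.5.1, guidance for Grade 2 or higher effusion, edema or hypoalbuminemia | Yes, but the same section asks that other causes be ruled out |
| Protocol Table 5-2, all other rows | No relatedness condition stated |
| Protocol 7.6.1.1, recording of AEs from Day 1 through the reporting period | No |
| Protocol 7.6.1.4, SAE report to the sponsor within 24 hours | No |
| SAP 7.7.1, all-causality AE and SAE tables, including events leading to discontinuation or death | No |

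The first two rows carry most of the consequence. The SAP describes no later re-adjudication of the investigator's call.

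**The case against.** The strongest reply is that these are examples and the tests themselves are sound. Unrelated rests on another cause being more plausible. Related rests on evidence of a causal link, and its list is open-ended. An investigator who knows from Section 1.1.3 that nausea is frequent with this drug may call it Related. That stands, and it limits the point to steering. A reader might infer that the rule forces an Unrelated call; the text does not say so.

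A second reply is that the study population could mean patients with this disease in general, which would make commonness a fair reference to background rate. The protocol does not define the term that way. On that reading the phrase adds little to the underlying-disease example beside it, and a common background still does not exclude a drug contribution.

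Third, drug-specific text works against the lean for some events. Section 5.5.1 says effusions and edema have been seen with the drug and asks that alternatives be excluded, and Section 5.5.2 directs evaluation of skin reactions. A reader might infer that the bias is greatest for effusions and edema, or that it reaches dose reduction generally. The documents do not support either: the Table 5-2 rows for effusion and edema state no relatedness condition, and only one laboratory row does.

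Fourth, safety assessment does not rest on relatedness alone. The plan has all-causality tables, adverse events of special interest found by search criteria, laboratory and pericardial-effusion shift tables, a listing of on-study deaths, and data monitoring committee review of safety about every 6 months. It would be too strong to call investigator relatedness the trial's main means of attributing harm.

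**Conclusion.** The concern holds as a drafting defect with a known direction and an unknown size. The examples lean toward Unrelated for drug effects shared with the disease, chiefly fatigue, dyspnea and nausea. The consequence falls mainly on the drug-related summaries and on late SAEs; the laboratory trigger and the effusion guidance are lesser users of the call.

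The conclusion assumes that these three events are common among the treated subjects and also arise from the disease. The documents do not give their frequency in this population. It also assumes that printed examples influence a two-way choice made across many sites.

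A reader might want a figure for how far drug-related rates would be understated. The documents give neither event rates nor the share caused by the drug, nor any misclassification rate, so such a figure would be wholly assumed and none is offered. Events that are rare apart from the drug, such as photosensitivity, are probably little affected. The point justifies a wording correction; it does not undermine the all-causality safety analysis.

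**What to change.** In Protocol Section 7.6.1.1:

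- Delete the commonness half of the Unrelated example and keep the underlying-disease half. Alternatively, add a sentence saying that commonness in the study population does not by itself make an event Unrelated.
- Add a third Related example: a known or suspected effect of study drug, even when such events also occur with the underlying disease.
- Leave both tests as they stand: evidence of a causal link for Related, and a more plausible other cause for Unrelated. Moving Related to a broader standard, such as reasonable possibility, is a separate preference and is not needed to close this gap.

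The cost is a protocol wording change and a memo to sites. Some drug-related counts may be higher as a result. No dose or clinical management rule needs to change.

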7.6.1.2 Procedures for Eliciting and Recording Adverse Events

Investigator and study personnel will report all AEs and SAEs whether elicited during subject questioning, or discovered during physical examination, laboratory testing and/or other means by recording them on the CRF and/or SAE form, as appropriate.

Eliciting Adverse Events

An open-ended or non-directed method of questioning should be used at each study visit to elicit the reporting of AEs.

Recording Adverse Events

The following information should be recorded on the Adverse Events and Pre-existing Conditions CRF:

- Description using standard medical terminology (with an effort to use the unifying or reached diagnosis), including onset and resolution dates
- Whether the AE met serious criteria
- Severity/Grade
- Relationship to study treatment or other causality
- Outcome

Diagnosis vs. Signs or Symptoms

In general, the use of a unifying or reached diagnosis is preferred to reporting of individual symptoms. Grouping of symptoms into a diagnosis should only be done if each component sign and/or symptom is a medically confirmed component of a diagnosis as evidenced by standard medical practice. If any aspect of a sign or symptom does not fit into a classic pattern of the diagnosis, report the individual symptom as a separate adverse event.

Important exceptions for this study are adverse reactions associated with the infusion of study drug. For infusion-related reactions, do not use the NCI CTCAE terms of ‘cytokine release syndrome,’ ‘acute infusion reaction,’ or ‘allergic or hypersensitivity reaction.’ Instead, record each sign or symptom as an individual AE. If multiple signs or symptoms occur with a given infusion-related event, each sign or symptom should be recorded separately with its own level of severity.

Recording Serious Adverse Events

For SAEs, record the event(s) on both the CRF and an SAE form.

The following should be considered when recording SAEs:

Death is an outcome of an event. Death, per se, is not a reportable event. The event that resulted in the death should be recorded and reported on both an SAE form and CRF.

For hospitalizations, surgical, or diagnostic procedures, the illness leading to the surgical or diagnostic procedure should be recorded as the SAE, not the procedure itself. The procedure should be captured in the narrative as part of the action taken in response to the illness.

Progression of the Underlying Cancer

Do not use the term ‘disease progression’ alone when reporting AEs, including SAEs, because it is too nonspecific. Symptoms of disease progression that meet the criteria for a SAE must be reported. When possible, report the specific disease (clinical) manifestation of the progression (e.g., ‘malignant pleural effusion,’ ‘spinal bone metastases,’ ‘lymphadenopathy,’ ‘brain metastases’).

Pregnancy

Notification to Drug Safety: Complete a Pregnancy Report Form for all pregnancies that occur from the time of first study drug dose until 6 months after the last dose of study drug(s) received, including any pregnancies that occur in the female partner of a male study subject. Additionally, report pregnancies that occur in a dosed male subject’s female partner if the estimated date of conception occurred after the male subject’s first dose of study drug. Transmit the form to the Drug Safety Department of the sponsor or designee within 48 hours of becoming aware of the pregnancy. All pregnancies will be monitored for the full duration; all perinatal and neonatal outcomes should be reported. Infants should be followed for a minimum of 8 weeks after their delivery.

Collection of data on the CRF: All pregnancies (as described above) that occur within 30 days of the last dose of study drug(s) will also be recorded on the Adverse Events and Pre-Existing Conditions CRF.

Abortion (whether spontaneous, therapeutic, or planned) should be reported as a SAE. Congenital anomalies or birth defects, as defined by the ‘serious’ criterion above (see definitions Section [7.6.1.1](#)) should be reported as SAEs.

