- b. Immune-checkpoint inhibitors (i.e., anti-PD-1, anti-PD-L1, or anti-CTLA-4): 4 weeks
- c. Other monoclonal antibodies, antibody-drug conjugates, radioimmunoconjugates, or T-cell or other cell-based therapies: 4 weeks (2 weeks with documented disease progression)

11. Females of childbearing potential must have a negative beta human chorionic gonadotropin (β -hCG) pregnancy test result within 7 days prior to the first dose of study drug. Females of non-childbearing potential are those who are postmenopausal greater than 1 year or who have had a bilateral tubal ligation or hysterectomy.

- a. Females of childbearing potential and males who have partners of childbearing potential must agree to use an effective contraception method during the study and for 1 year following the last dose of study drug. Effective birth control includes (a) combined, estrogen and progestogen containing, hormonal contraception (oral, intravaginal, transdermal); (b) progestogen-only hormonal contraception (oral, injectable, implantable); (c) intrauterine device (d) intrauterine hormone-releasing system; (e) bilateral tubal occlusion; (f) vasectomised partner; and (g) sexual abstinence.

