Note: The term “life-threatening” in the definition of “serious” refers to an event in which the patient was at risk of death at the time of the event; it does not refer to an event which hypothetically might have caused death if it were more severe.

Hospitalization:	Requires in-patient hospitalization, or resulted in prolongation of an existing hospitalization, (Hospitalizations for elective medical or surgical procedures or treatments planned before the signing of informed consent in the study or routine check-ups are not SAEs by this criterion. Admission to a palliative unit or hospice care facility is not considered to be a hospitalization. Hospitalizations or prolonged hospitalizations for scheduled therapy of the underlying cancer or study target disease need not be captured as SAEs).
Disabling/ incapacitating:	Resulted in a persistent or significant disability/ incapacity or substantial disruption of the subject's ability to conduct normal life functions.
Congenital anomaly or birth defect:	Is a congenital anomaly or birth defect in a child or fetus of a patient/subject who has been exposed to the molecule or study treatment regimen before conception or during pregnancy.
Medically significant:	The AE did not meet any of the above criteria, but could have jeopardized the subject and might have required medical or surgical intervention to prevent one of the outcomes listed above or involves suspected transmission via a medicinal product of an infectious agent.

The following hospitalizations will not be considered SAEs:

- A visit to the emergency room or other hospital department of less than 24 hours, that does not result in a hospital admission (unless considered an important medical event or a life-threatening event)
- Elective surgery, that was planned prior to signing consent
- Admissions, per protocol, for a planned medical/surgical procedure
- Scheduled therapy of the underlying cancer or study target disease
- Routine health assessments (e.g., routine colonoscopy)

Admission to a palliative unit or hospice facility is not considered a hospitalization.

Adverse Event Severity

AE severity should be graded using the National Cancer Institute's Common Terminology Criteria for Adverse Events (NCI CTCAE), version 4.03. These criteria are provided in the study manual. When CTCAE grade is not available, severity will be used.

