7.6.1.4 Serious Adverse Events Require Immediate Reporting

Within 24 hours of observing or learning of a SAE, investigators are required to report the event to the sponsor or designee, regardless of the relationship of the event to the study treatment regimen.

For initial SAE reports, available case details are to be recorded on a SAE form. At a minimum, the following must be included:

- Identifiable subject with identification number (can also include gender, age at onset)
- Study treatment (suspect medicinal product)
- Identifiable reporting source
- An event or outcome that can be identified as serious, preferably with a description of the event with date of event onset (to reflect latency)
- Causality (relatedness)

The completed SAE form are to be transmitted to the Drug Safety Department of the sponsor or designee (see contact information specified on the SAE report form) within 24 hours.

Relevant follow-up information is to be submitted to the sponsor as soon as it becomes available.

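### Pregnancy reporting for female subjects stops 6 months after the last dose while contraception is required for 1 year, so an uncomplicated pregnancy beginning in months 6-12 has no explicit notification rule

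*Protocol*

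**What the plan says.** **Contraception.** Protocol Section 4.1, criterion 11a: women who could become pregnant, and men whose partners could, "must agree to use an effective contraception method during the study and for 1 year following the last dose of study drug". Criterion 11 says who is outside the group: "Females of non-childbearing potential are those who are postmenopausal greater than 1 year or who have had a bilateral tubal ligation or hysterectomy".

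**Pregnancy reporting.** Protocol Section 7.6.1.2, under Pregnancy:
- The Pregnancy Report Form is due for pregnancies from the first dose "until 6 months after the last dose of study drug(s) received", and must reach the sponsor's drug safety group within 48 hours of awareness.
- A further sentence makes a pregnancy in a male subject's partner reportable "if the estimated date of conception occurred after the male" subject's first dose. It has no end date.
- Recording on the adverse event CRF is limited to 30 days after the last dose.
- Pregnancies are to be followed to their end, with perinatal and neonatal outcomes reported. This sentence has no window of its own.
- "Abortion (whether spontaneous, therapeutic, or planned) should be reported as a SAE", and congenital anomalies are likewise SAEs. No end date is attached.

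**SAE rules.** The congenital anomaly criterion in Section 7.6.1.1 covers the child of a subject "exposed to the molecule or study treatment regimen before conception or during pregnancy". Under Section 7.6.1.4, investigators learning of an SAE are "required to report the event to the sponsor or designee, regardless of the relationship of the event to the study treatment regimen". Section 7.6.1.3 closes the safety reporting period 30 days after the last dose and adds that later SAEs "considered study treatment-related in the opinion of the investigator should also be reported".

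**Follow-up.** The last scheduled pregnancy test is at the End of Treatment visit (Section 6.4). Long-term follow-up collects disease assessments, later therapies, progression and survival (Section 6.5; Section 12.1, note 21), with no pregnancy item. The SAP has no rule on pregnancy reporting.

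**The concern.** The protocol treats the whole year after the last dose as a period in which pregnancy must be avoided, yet asks for a report of a female subject's pregnancy only in the first half of it. No reason is given for the shorter window. A woman who received the drug herself is also covered for less time than the partner of a man who received it, which looks like an oversight.

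The payload is a DNA cross-linking agent (Section 1.1.2). If late abnormal outcomes arrive through the SAE rules while late normal pregnancies go unreported, there are adverse outcomes with no denominator, and no data on whether a 1-year contraception period is adequate. This is a matter of safety data only.

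**Working it through.** The documents give no figure to reproduce. The check is a comparison of time windows, followed by an illustration of size.

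**1. Which rule covers a female subject's pregnancy, by when it begins after the last dose**

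| Rule | Months 0-6 | Months 6-12 |
|---|---|---|
| Contraception (4.1, 11a) | required | required |
| Pregnancy Report Form, 48-hour notice (7.6.1.2) | required | not required |
| CRF record (7.6.1.2) | first 30 days only | no |
| Partner sentence (7.6.1.2) | does not apply to female subjects | does not apply to female subjects |
| Abortion or anomaly as SAE (7.6.1.1 to 7.6.1.4) | yes | at least partly |
| Scheduled pregnancy test (6.4) | to End of Treatment | none |
| Follow-up contact items (6.5; 12.1, note 21) | no pregnancy item | no pregnancy item |

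Gap: 12 - 6 = 6 months. For male subjects' partners it is 0. Retreatment moves the last dose for both windows together, so the gap stays at 6 months.

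**2. The abortion and anomaly row.** Sections 7.6.1.1, 7.6.1.2 and 7.6.1.4 read together capture these outcomes without an end date. Section 7.6.1.3 can be read to limit SAEs after 30 days to those judged treatment-related. On either reading some are reportable. An uncomplicated pregnancy meets no SAE criterion, so it is reportable on neither.

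**3. Calendar size on the planned two-dose schedule** (second dose 42 days after the first; 30.44 days per month)
- Form window closes: 42 + 182.6 = day 224.6, month 7.38.
- Contraception ends: 42 + 365.25 = day 407.25, month 13.38.
- Gap: 182.6 / 407.25 = 45% of calendar time from first dose.

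**4. Person-time size.** The 45% counts everyone as alive throughout. Assume exponential survival from first dose with median m months, S(t) = 2^(-t/m). Section 1.1.1 gives a median below 6 months for recurrent disease. The gap's share of person-time is [S(7.38) - S(13.38)] / [1 - S(13.38)].

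| m (months) | S(7.38) | S(13.38) | Share |
|---|---|---|---|
| 4 | 0.28 | 0.10 | 20% |
| 5 | 0.36 | 0.16 | 24% |
| 6 | 0.43 | 0.21 | 27% |

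Per 10 females of childbearing potential treated, that is 2.8-4.3 alive when the gap opens, 1.0-2.1 alive when it closes, and 0.9-1.5 person-years inside it. With the 13.9-week median that Section 1.1.1 quotes for best supportive care (about 3.2 months), the share is about 16%. The documents do not say how many such women will be treated, so no expected number of pregnancies can be derived.

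**The case against.** **Another sentence may already cover it.** Section 7.6.1.2 says pregnancies are to be followed to their end and outcomes reported, with no time limit. That sentence comes after the form and 48-hour rules, sets no notification window, and most naturally means the pregnancies reported under those rules. It weakens any absolute claim that nothing applies, but it does not supply a notification requirement.

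**The outcomes that matter most are covered elsewhere.** This largely stands. A reader might infer that all late outcomes in female subjects escape reporting. The documents do not support that: abortion and congenital anomaly are SAEs, the anomaly criterion includes exposure before conception, and even the narrow reading of Section 7.6.1.3 keeps treatment-related events reportable indefinitely.

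**Not every pregnancy seen in months 6-12 is affected.** Correct. The form rule depends on when the pregnancy occurs, so one that began in month 5 and came to light in month 8 is still reportable.

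**The two windows need not match.** No text says they must, and no analysis uses pregnancy data. This argues for low severity. It does not explain why dosed women have the shorter window.

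**Unseen manuals may fill the gap.** Possible. The SAE reporting manual and the study manual are mentioned but not included, so the protocol text can be shown to have a gap, but not that data would be lost in practice.

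**Conclusion.** The mismatch is real and narrow. It concerns uncomplicated pregnancies in female subjects of childbearing potential that begin more than 6 and up to 12 months after the last dose. For these the protocol has no explicit notification requirement.

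In size it is half of the post-dose contraception year. A reader might take the 45% of calendar time as the share of exposure left unmonitored. That overstates it: because survival is short, the share of person-time is about 20-27% under the assumed medians of 4 to 6 months. Those figures rest on the exponential form and on a median given for recurrent disease generally rather than for third-line and later treatment. Nor do the documents support extending the point to male subjects' partners.

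Very few cases are expected and no efficacy result changes. Severity is low. The point is worth making because the correction is almost free.

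**What to change.** In Protocol Section 7.6.1.2, in the sentence containing "until 6 months after the last dose of study drug(s) received", change 6 months to 1 year. The uncovered interval for female subjects falls from 6 months to 0. Leave the partner sentence unchanged. No retreatment wording is needed, because the last dose already moves with retreatment.

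Optionally, add a pregnancy question for females of childbearing potential at the existing long-term follow-up contacts that cover that year. Counting contacts from the last dose (an assumption for subjects already past progression) gives weeks 6, 12, 18, 24, 36, 48 and 60. Weeks 36 and 48 fall inside the gap, which runs from week 26.1 to week 52.2. Week 60 is needed for the last 29 days of the year (365.25 - 336; 16% of the gap). This is extra surveillance and is not needed to align the windows.

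Cost: one phrase for the main change. The option adds a line in Section 6.5, an edit to note 21 in Section 12.1 and one item on the follow-up form. There are no new visits. The downside is a few extra reports.
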